6.2.2.4 Donepezil Dose Selection

Donepezil is a marketed drug and has been widely used in the human population at a 5 mg oral dose, which is the lowest dose level used in the treatment of AD. In addition, nonclinical studies show that TAK-071 has the potential to be efficacious in a scopolamine-induced cognitive deficit model in the presence of low/suboptimal donepezil doses due to synergistic effects. TAK-071 will likely be used as add-on therapy in subsequent clinical studies; consequently, it is relevant to study the lower standard dose of donepezil. Due to the plasma half-life of donepezil (>70 hours), it is necessary to pretreat subjects with donepezil for 3 weeks to ensure that steady-state concentrations have been reached prior to dosing with TAK-071. Although donepezil is available at higher strengths (10 and 23 mg), there is an increased incidence of side effects, including nausea, vomiting, and diarrhea, at these dose levels. Consequently, it is not suitable to provide a loading dose to facilitate reaching the desired plasma concentrations in a shorter time interval.

A dose of 5 mg QD has been selected for the healthy subject cohorts (10 to 12) because the target population of patients with AD is known to better tolerate cholinomimetic treatments as compared with healthy young adults [12]; thus, a dose of 5 mg is thought to be appropriate for the purposes of an initial evaluation of the safety, tolerability, and PK of the donepezil plus TAK-071 combination. Because PK sampling for donepezil plasma concentrations will be performed in these cohorts, for practical purposes and to avoid PK sampling overnight, donepezil dosing will occur in the morning simultaneously with TAK-071. This will also provide an opportunity to evaluate the potential for a drug-drug interaction of TAK-071 on donepezil while at steady-state. For this reason, the exact dosing time of donepezil relative to TAK-071 will be selected so as to ensure that both drugs attain their peak concentrations at approximately the same time to maximize the potential for interaction. Donepezil is reported to have a t_{max} of 3 to 4 hours, and preliminary TAK-071 PK data from SRD Cohorts 1 to 4 indicates that maximum, or near maximum, plasma concentrations are attained approximately 4 hours postdose; thus, donepezil should be dosed approximately 1 hour after TAK-071; however, the definitive dosing time of donepezil relative to TAK-071 will be confirmed following evaluation of all preliminary PK data from the SRD part of the FIH study.

According to the donepezil (Aricept) product label, the recommended starting dosage of donepezil is 5 mg administered once per day in the evening, just prior to retiring. The maximum recommended dosage in patients with mild-to-moderate AD is 10 mg per day. A dose of 10 mg should not be administered until patients have been on a daily dose of 5 mg for 4 to 6 weeks. Because the majority of patients with mild AD are prescribed donepezil 10 mg QD, 10 mg has been selected as the donepezil dose for Cohort 16. To minimize variability, subjects who are regularly taking this dose in the evening, as recommended in the product labeling [11], will be recruited into the study. This will also provide safety and tolerability data for the combination treatment in the intended target population under realistic dosing regimen conditions and will also provide data at a higher donepezil dose than that tested in the preceding healthy subject cohorts.

Donepezil has been previously administered to healthy subjects in the context of multiple phase 1 clinical trials, indicating that single doses of 10 mg are safe and well tolerated in this population [19-22]. In particular, donepezil doses of both 5 and 10 mg have been employed in published

[21,22] and unpublished (Study ROF-ALZ_102) scopolamine challenge studies. The higher 10 mg dose is therefore expected to maximize the chances of a successful positive control in Cohorts 20 to 22.

6.2.3 Endpoints

The SRD/MRD cohorts (Cohorts 1 to 15, and 18 to 22) will be conducted in healthy subjects to collect safety and tolerability information that will not be biased by any comorbidity and other intrinsic/extrinsic factors. The safety and tolerability will then be investigated in subjects with MCI or mild AD (Cohort 16) at doses with an acceptable safety profile in the healthy subject cohorts. The safety endpoints include AEs, vital signs, weight, ECG findings, and laboratory test results. In addition, bowel function will be assessed (eg, BSF scale) to further investigate the potential cholinomimetic effects on the gastrointestinal (GI) tract.

The plasma concentration of TAK-071 will be examined to characterize the PK of TAK-071 following single and multiple doses. Determination of TAK-071 PK in this study will also enable the evaluation of the effect of ethnicity on PK as well as exploration of the comparability of PK between the target population (patients with AD) and healthy subjects.

Currently available in vitro data indicate there is a low potential for PK drug-drug interaction of TAK-071 on donepezil via CYP enzymes. The determination of donepezil plasma concentrations will enable the investigation of any effect of TAK-071 on donepezil PK via any other unaccounted for mechanisms prior to dosing subjects with MCI or mild AD. The effect of donepezil on TAK-071 PK will also be explored.

The investigation of CSF concentrations of TAK-071 is intended to establish some understanding of the approximate level of brain penetration relative to plasma for TAK-071 itself, which will be helpful for guiding dose selection within the present study and for the interpretation of future studies.

The M3 receptor, rather than M1, is the most abundant postjunctional receptor and is thought to be the most important muscarinic receptor subtype for mediating pupil contraction. Because TAK-071 selectively modulates M1 activity, changes in pupil size following TAK-071 treatment are not expected [16]. However, this evaluation will allow confirmation of the lack of engagement with other muscarinic receptors in a clinical setting.

CCI

6.3 Premature Termination or Suspension of Study or Investigational Site

6.3.1 Criteria for Premature Termination or Suspension of the Study

The study will be completed as planned unless one or more of the following criteria are satisfied that require temporary suspension or early termination of the study.

- New information or other evaluation regarding the safety or efficacy of the study drug that indicates a change in the known risk/benefit profile for the product, such that the risk is no longer acceptable for subjects participating in the study.
 - Significant violation of Good Clinical Practice (GCP) that compromises the ability to achieve the primary study objectives or compromises subject safety.
 - Study-specific criteria for terminating the study (eg, study meets predefined rule for futility or benefit, study meets predefined stopping rules within or between cohorts per Section 6.1.5).
 1. Dose escalation will be stopped if it is predicted that further dose escalation will not result in a further increase in plasma exposure (ie, an exposure ceiling is reached).
 2. Dose escalation will be stopped at a dose level (ie, 1 escalation step) below the dose that is predicted to give a TAK-071 AUC or C_{max} that exceeds that of the 28-day monkey toxicology study NOAEL.
 3. Two or more subjects in any single cohort or across more than 1 cohort experience any of the Takeda Medically Significant List events (as outlined in Table 10.a).*
 4. Two or more subjects in any single cohort or across more than 1 cohort experience alanine aminotransferase (ALT) and/or aspartate aminotransferase (AST) elevations $>5\times$ upper limit of normal (ULN) in the absence of a concomitant bilirubin increase [see point 5 below].*
 5. One or more subjects in any single cohort or across more than 1 cohort experience ALT and/or AST elevations $>3\times$ ULN in the presence of a total bilirubin increase $>2\times$ ULN or an international normalized ratio (INR) >1.5 without findings of cholestasis or other alternate etiology to explain the elevations (ie, “Hy’s Law cases”).
 6. Two or more subjects in any single cohort or across more than 1 cohort experience ALT and/or AST elevations $>3\times$ ULN with the appearance of fatigue, nausea, vomiting, right upper quadrant pain or tenderness, fever, rash, and/or eosinophilia ($>5\%$).*
- * Please note that the study may be terminated early prior to full attainment of these criteria (eg, if just 1 subject experiences 1 of these events) if warranted by safety data from the other subjects dosed in the study to date.
7. Two or more subjects in any single dose cohort show a shift in safety EEG electroclinical assessment from rating (grading) 0 to 2, or any of the subjects shows clinical signs of clinically manifest convulsive or non-convulsive seizure activity.

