It is planned that Cohort 2 plasma samples (post-24 hours) will be analyzed separately and will not comprise part of the dose escalation PK datasets.

For illustration purposes, and based on human PK predictions using animal data, the planned dose escalation in the SRD is as follows: 1, 3, 9, 20, 40, and 50 mg. However, based on emerging safety and PK data from Cohort 1 through 6, 18, and 19, doses of 80, 60, and 40 mg are planned for Cohorts 20 to 22 to understand safety and tolerability of TAK-071+donepezil (10 mg). The TAK-071 plasma exposure following an 80 mg TAK-071 + 10 mg donepezil dose is predicted to be approximately equivalent to 15 mg TAK-071 + 5 mg donepezil in chronic administration in the MRD study, and this dose was well-tolerated in Cohort 12. A dose of 160 mg TAK-071 + 10 mg donepezil will provide an approximate 1.5-fold increase in TAK-071 exposure compared to the 80 mg TAK-071 + 10 mg donepezil dose. The dose selected for Cohort 21 will be not higher than 160 mg and will be based on the safety data from TAK-071 120 mg dose.

It is planned that the MRD cohorts will start no sooner than after all subjects in the SRD Cohort 4 have been dosed. The starting dose of the MRD cohorts will then be decided following a review of the blinded 24-hour safety (AEs, vital signs, ECG, clinical laboratory results) and tolerability from

Cohort 4 and the 24-hour preliminary plasma PK and 12-hour CSF PK data from Cohort 3. Under no circumstances will the starting dose for MRD Cohort 7 exceed that of the immediately preceding cohort for which blinded 24-hour safety and tolerability data have been evaluated and deemed to be acceptable. For example, safety and tolerability data from Cohort 4 would enable a maximum starting MRD dose analogous to Cohort 3. In the unlikely event that CSF concentrations are found to be low, ie, the majority of time points are below the limit of quantification, the MRD start may be postponed until a single dose that provides acceptable CSF concentrations is identified.

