7.2.1 Additional Exclusion Criteria for Cohorts With CSF Collection

1. The subject has had CSF collection performed within 30 days prior to Check-in.
2. The subject has a known hypersensitivity to the anesthetic or its derivatives used during CSF collection or any medication used to prepare the area of lumbar puncture.
3. The subject has significant vertebral deformities (scoliosis or kyphosis) that, in the opinion of the investigator, may interfere with the lumbar puncture procedure.
4. The subject has a history of clinically significant back pain and/or injury in the opinion of the investigator.
5. The subject has local infection at the puncture site.
6. The subject has thrombocytopenia or other suspected bleeding tendencies noted before the procedure.
7. The subject has developed signs and symptoms of spinal radiculopathy, including lower extremity pain and paresthesias.
8. The subject has any focal neurological deficit that might suggest an increase in intracranial pressure.
9. The subject has any abnormal findings on ophthalmological assessment/funduscopy suggestive of raised intracranial pressure (ie, optic disc swelling/edema; or [uncontrolled] hypertensive retinopathy).

10. The subject suffers regularly from moderate-to-severe headaches requiring analgesics.

7.2.2 Additional Exclusion Criteria for Cohorts 18 to 22

1. Subjects with lifetime history of seizures, including but not limited to childhood febrile seizure.
2. Subjects with EEG abnormality at Screening of Category 2, exclusionary criteria defined in the EEG manual. Categories: 0 (within normal limits), 1 (mildly abnormal, not exclusionary) and 2 (abnormal, exclusionary).

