9.5 Blood Volume

Total blood sampling volume for an individual subject is shown in [Table 9.q](#) for Cohorts 1 to 6, 18, and 19; [Table 9.r](#) for Cohorts 7 and 8; [Table 9.s](#) for Cohorts 9 and 13 to 15; [Table 9.t](#) for Cohorts 10 to 12; [Table 9.u](#) for Cohort 16, and [Table 9.v](#) for Cohort 17, and [Table 9.w](#) for Cohorts 20 to 22.

Table 9.q Approximate Blood Volume for Cohorts 1 to 6, 18, and 19

Sample Type	Sample Volume (mL)	Number of Samples							Final Visit Day 5	PK Follow-Up Day 8	Total Volume (mL)
		Screening	Day -1	Day 1 (a)	Day 2	Day 3	Day 4	Day 5			
Clinical laboratory tests	20	1	1	1	1	1	1	1	1	160	
Serology tests	8.5	1	0	0	0	0	0	0	0	8.5	
PGx DNA sample collection	6	0	0	1	0	0	0	0	0	6	
PGx RNA sample collection	2.5	0	0	4	0	0	0	2	0	15	
PK blood collection (b)	3	0	0	13	1	1	1	1	1	54	
Total Approximate Blood Sampling Volume										243.5	

(a) TAK-071 dose.

(b) For Cohorts 18 and 19, PK blood samples were as follows: Day 1: 9, Day 2: 3, Day 3: 1, Day 4: 1, Day 5: 1, and Day 8: 1 (Total volume 54 mL).

Table 9.r Approximate Blood Volume for Cohorts 7 and 8

Sample Type	Sample Volume (mL)	Number of Samples									Total Volume (mL)
		Screening	Day -1	Day 1 (a)	Day 2	Days 4-5	Days 8-20	Day 21 (b)	Day 22	Final Visit Day 23	
Clinical laboratory tests	20	1	1	1	1	1 (c)	3 (d)	1	1	1	220
Serology tests	8.5	1	0	0	0	0	0	0	0	0	8.5
PGx DNA sample collection	6	0	0	1	0	0	0	0	0	0	6
PGx RNA sample collection	2.5	0	0	4	0	0	0	2	0	0	15
PK blood collection	3	0	0	13	1	0	4 (e)	13	1	0	96
Total Approximate Blood Sampling Volume											345.5

- (a) First dose of multiple daily TAK-071.
- (b) Last dose of multiple daily TAK-071.
- (c) Blood sample on Day 5.
- (d) Blood samples on Days 8, 14, and 20.
- (e) Blood samples on Days 8, 14, 19, and 20.

Table 9.s Approximate Blood Volume for Cohorts 9 and 13 to 15 (Japanese)

Sample Type	Sample Volume (mL)	Number of Samples										Final Visit Day 30	Total Volume (mL)
		Screening	Day -1	Day 1 (a)	Day 2	Days 3-7	Day 8 (b)	Days 9-17	Days 18-27	Day 28 (c)	Day 29		
Clinical laboratory tests	20	1	1	1	1	1 (d)	1	3 (e)	2 (f)	1	1	1	280
Serology test	8.5	1	0	0	0	0	0	0	0	0	0	0	8.5
PGx DNA sample collection	6	0	0	1	0	0	0	0	0	0	0	0	6
PGx RNA sample collection	2.5	0	0	2	0	0	2	0	0	2	0	0	15
PK blood collection	3	0	0	13	1	3 (g)	13	3 (h)	3 (i)	13	2 (j)	0	147
Total Approximate Blood Sampling Volume												456.5	

Note: There is a 7-day washout between the single dose of TAK-071 and the first dose of multiple-dose TAK-071.

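### If rule 7 uses the Screening EEG categories, its EEG-shift limb cannot count a subject who enters at Category 1 and worsens to 2

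*Protocol*

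**What the plan says.** Protocol Section 6.3.1 lists criteria that require suspension or termination when met. Rule 7 has two limbs. The EEG limb needs at least two subjects in a single dose cohort with a "shift in safety EEG electroclinical assessment from rating (grading) 0 to 2". The seizure limb is met by any one subject with clinical signs of convulsive or non-convulsive seizure activity.

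Section 7.2.2 sets the EEG entry criterion for Cohorts 18 to 22. It excludes "Subjects with EEG abnormality at Screening of Category 2", with details left to the EEG manual. Category 0 is within normal limits, and the other two labels read "1 (mildly abnormal, not exclusionary) and 2 (abnormal, exclusionary". Category 1 is therefore admissible.

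The note under the Section 6.3.1 rules says that "the study may be terminated early prior to full attainment of these criteria". Its asterisk is attached to rules 3, 4 and 6. Rule 7 carries none.

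**The concern.** The EEG limb depends on where a subject starts. Rules 3 to 6 do not: they use events or absolute thresholds and count every subject whatever the baseline. A subject admitted at Category 1 who reaches the level that would have barred entry is not described by the words of the EEG limb.

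The stake is an early warning. The seizure limb, and convulsive seizure under rule 3 through Table 10.a, act only once a seizure is clinically apparent, whereas an EEG trigger can act before that. Cohorts 20 to 22 add donepezil 10 mg, and Section 4.3 anticipates possible synergy between the two drugs. Section 11.0 provides no independent monitoring committee, so prespecified triggers carry more weight than they otherwise would.

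**Working it through.** The documents give no operating characteristic for rule 7, so there is no figure to reproduce. The check is a reading of rule 7 against Section 7.2.2.

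**Step 1: individual shifts, assuming one shared 0/1/2 scale and a starting rating equal to the entry category.**
- Start 0, reach 2: counted.
- Start 0, reach 1: not counted.
- Start 1, reach 2: not counted.
- Start 2: not admitted in Cohorts 18 to 22.

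**Step 2: two subjects in one dose cohort both reach 2, neither with seizure signs.**
- Both started at 0: the limb is met.
- One started at 0 and one at 1: not met.
- Both started at 1: not met.

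So the wording covers one of the three starting combinations. These are not equally likely, and the documents do not say how often each would arise.

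**Step 3: what else could stop dosing in the two uncovered combinations.**
- Sentinel review in Cohorts 20 to 22 (Section 6.1.1): three subjects are dosed and their 24-hour data reviewed before the other nine.
- Cohort review (Section 6.1.5), including the provision that the study stops if investigator and sponsor cannot agree on escalation.
- The general criterion in Section 6.3.1 for new information that "indicates a change in the known risk/benefit profile for the product".
- The veto in Section 11.0.

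Each needs someone to judge that the EEG change matters. None is a prespecified EEG trigger.

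**Step 4: which cohorts are still affected.**
- Cohorts 18 and 19 appear already dosed. Section 6.2.2.2 plans the doses of Cohorts 20 to 22 "based on emerging safety and PK data from Cohort 1 through 6, 18, and 19", and the footnote to Table 9.q says "For Cohorts 18 and 19, PK blood samples were as follows". Against this, Section 6.2.2.2 still describes the 120 mg dose in Cohort 18 as planned.
- Cohorts 20 to 22 are planned at 80, 60 and 40 mg, subject to emerging data. Section 6.2.2.2 also says "The dose selected for Cohort 21 will be not higher than 160 mg". The documents do not say whether Cohort 20 or 21 had been dosed by this amendment.
- Section 6.1 allows further single-dose cohorts, but Section 7.2.2 names only Cohorts 18 to 22. An added cohort is affected only if it takes over the same EEG entry criterion.

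**Step 5: size.** The number of Category 1 entrants and the risk of worsening to 2 are not given. Any probability would rest on two invented inputs, so none is offered.

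**The case against.** The strongest objection is that the premise lies in text nobody outside the sponsor can read. Rule 7 speaks of an electroclinical assessment with a rating; Section 7.2.2 speaks of Screening categories with eligibility labels. No visible sentence links them, and the on-study definition may sit in the EEG manual or the blacked-out EEG text. This stands. It makes the point conditional and puts the manual check before any rewording.

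A second objection is that a two-grade change may be the intended threshold, since 0 to 1 is left out as well. That is possible, but no visible text says so. On a three-grade scale it would also put the limb out of reach for subjects the protocol chose to admit.

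A third is that ample backstops exist. A reader might infer that EEG worsening in Category 1 entrants could go unchecked. The documents do not support that: the routes in Step 3 are real, the seizure limb ignores starting grade, and Section 6.1.5 adds criteria for discontinuing cohort entry after drug-related events. Nor does the missing asterisk on rule 7 prevent an earlier stop, because the risk/benefit criterion remains available. What these routes lack is a prespecified EEG threshold.

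A reader might also infer a measurable loss of sensitivity, or that every added single-dose cohort is affected. Neither follows. The Category 1 share is unknown, and Section 7.2.2 does not name added cohorts.

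**Conclusion.** The point holds conditionally. If the rule 7 rating is the Section 7.2.2 scale, the EEG limb omits worsening from 1 to 2 although Category 1 entry is allowed, and a stop without clinical seizure signs would rest on judgment.

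It depends on three assumptions: the scales are the same; the on-study rating is not set relative to each subject's own baseline, which would remove the gap; and a Category 1 entrant's starting rating remains 1. The size cannot be estimated. It is zero if no Category 1 subject enters a cohort still to be dosed. A definite defect in the stopping rule is more than the visible text can establish.

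**What to change.** First, confirm against the EEG manual that the on-study rating and the Screening category are the same scale, and that the on-study rating is not relative to the subject's own baseline. State the result in rule 7.

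If both are confirmed, replace "shift in safety EEG electroclinical assessment from rating (grading) 0 to 2" with: shift in safety EEG electroclinical assessment to rating 2 from a baseline rating of 0 or 1. Keep the requirement of two or more subjects in a single dose cohort, and leave the seizure limb unchanged. All three starting combinations in Step 2 would then meet the limb.

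The cost is one check and one reworded sentence, using ratings already collected. The downside is a somewhat higher chance of a temporary suspension from a one-grade change in subjects who were mildly abnormal at entry. If the check shows different scales or a baseline-relative rating, a clarifying sentence in rule 7 is enough.

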6.3.2 Criteria for Premature Termination or Suspension of Investigational Sites

A study site may be terminated prematurely or suspended if the site (including the investigator) is found in significant violation of GCP, protocol, or contractual agreement, is unable to ensure adequate performance of the study, or as otherwise permitted by the contractual agreement.

6.3.3 Procedures for Premature Termination or Suspension of the Study or the Participation of Investigational Site(s)

In the event that the sponsor, an institutional review board (IRB), or regulatory authority elects to terminate or suspend the study or the participation of an investigational site, a study-specific procedure for early termination or suspension will be provided by the sponsor; the procedure will be followed by applicable investigational sites during the course of termination or study suspension.

7.0 SELECTION AND DISCONTINUATION/WITHDRAWAL OF SUBJECTS

All entry criteria, including test results, need to be confirmed prior to randomization. For Cohorts 10 to 12, check-in occurs on Day -22 for all eligibility criteria.

7.1 Inclusion Criteria

Subject eligibility is determined according to the following criteria prior to entry into the study:

1. In the opinion of the investigator, the subject is capable of understanding and complying with protocol requirements.
2. The subject or, when applicable, the subject's legally acceptable representative signs and dates a written informed consent form (ICF) and any required privacy authorization prior to the initiation of any study procedures including requesting that a subject fast for any laboratory evaluations.
3. The subject is a healthy man or woman. Subjects should be aged 18 to 55 years, inclusive (nonelderly at the time of informed consent and first study drug dose) for Cohorts 1 to 12, and 17 to 22; 20 to 55 years, inclusive, for Cohorts 13 to 15; and 55 to 90 years, inclusive, for Cohort 16.
4. The subject weighs at least 50 kg and has a body mass index (BMI) from 18.0 to 30.0 kg/m², inclusive, at Screening.
5. For Cohorts 13 to 15 only: First-generation Japanese, defined as having been born in Japan of Japanese parents and Japanese grandparents and living no more than 10 years outside of Japan, with no significant change in lifestyle, including diet, while living outside of Japan.
6. Cohort 16 only:
 - a) Subjects with a documented previous diagnosis of MCI or mild AD or current diagnosis of AD criteria met at Screening Visit.
 - b) Mini Mental State Examination (MMSE) score of 18 to 30, inclusive for subjects with existing diagnosis of MCI or mild AD or 18 to 26 inclusive for subjects diagnosed with mild AD at Screening and no biomarker data to contradict this diagnosis.
 - c) Retrospectively, or at Screening Visit, subjects will have met a diagnosis of probable AD based on the National Institute of Neurological Disorders and Stroke Alzheimer's Disease and Related Disorders Association criteria [17] or retrospective clinical diagnosis of MCI based on criteria such as subjective cognitive complaint, evidence of impairment in 1 or more cognitive domain, preservation of functions, and absence of dementia [18]. (Note: treatment can be initiated ONLY based on Mild AD Diagnosis at Screening Visit.)
 - d) Subjects must be receiving ongoing donepezil therapy (10 mg) in the evening for a minimum of 21 days prior to Check-in (Day -1).
7. A female subject with no childbearing potential, defined as subjects who have been surgically sterilized (hysterectomy, bilateral oophorectomy, or tubal ligation) or who are postmenopausal

(defined as continuous amenorrhea of at least 2 years and follicle-stimulating hormone [FSH] >40 IU/L).

8. A male subject who is nonsterilized* and sexually active with a female partner of childbearing potential* agrees to use adequate contraception* from signing of informed consent throughout the duration of the study and for 30 days after last dose.

*Definitions and acceptable methods of contraception are defined in Section 9.1.10 Contraception and Pregnancy Avoidance Procedure and reporting responsibilities are defined in Section 9.1.11 Pregnancy.

